**Phase 1 Study: Detection of Brown Adipose Tissue in Normal  
Volunteers Using a 3 Tesla (3T) Magnetic Resonance Imaging System  
and Hyperpolarized (HP) Xenon Gas**

**NCT number** NCT02220426  
**Document Date** 10/09/2014

**SPECIFIC AIMS:** In spite of the many efforts to raise awareness on the health complications of obesity, our obesity epidemic keeps growing, adding an immense cost to our health care system. At a fundamental level obesity is the result of an imbalance between energy intake and energy expenditure. The latter is very difficult to quantify and recent work suggests that in humans it is partially modulated by the activity of Brown Adipose Tissue (BAT). BAT is a tissue with the unique capacity to regulate energy expenditure by a process called thermogenesis during which this tissue burns fat to produce heat. By preventing excessive accumulation of triglyceride in non-adipose tissues such as muscle and liver, this tissue also helps to protect against insulin resistance and type 2 diabetes.

As ways to harness this tissue to address obesity and diabetes are being investigated, its non invasive detection in humans remains an unmet need. The current gold standard for the detection of BAT activity is FDG-PET. Unfortunately this technique has obvious limitations: 1) It cannot be used for longitudinal studies in healthy subjects due to concerns over radiation exposure, 2) It is not reproducible, and 3) It fails in detecting BAT in the target population, i.e. in overweight and obese subjects. Other imaging modalities like MRI and CT have been tried, but aside from lacking specificity and their inability to detect BAT activity, they all share the same insensitivity to the lipid rich BAT present in overweight and obese subjects.

The goal of the proposed application is to provide a non-invasive imaging tool that is suitable to detect mass and metabolic activity of BAT in both lean and obese human subjects. Our group was the first to demonstrate the use of hyperpolarized xenon gas MRI to specifically and directly detect BAT mass and thermogenic activity in lean and obese mouse phenotypes, with unprecedented sensitivity in the latter. The objective of the current proposal is to validate this technique in humans. To this end we propose the following aims:

**Specific Aim 1:** Demonstrate BAT mass detection in human subjects. For this aim we will implement hyperpolarized xenon imaging on our clinical scanner and we will compare the images obtained before stimulation of BAT thermogenesis with those obtained during stimulation of BAT thermogenesis. Our working hypothesis is that, during stimulation of BAT thermogenesis the lipophilic gas will accumulate in the highly perfused BAT tissue enabling us to clearly delineate it.

**Specific Aim 2:** Demonstrate detection of BAT thermogenesis in humans. For this aim we will measure BAT temperature by measuring the chemical shift of lipid-dissolved xenon. Our working hypothesis is that, during stimulation of BAT thermogenic activity, changes in BAT temperature would be detected as a shift in the resonance frequency of lipid-dissolved xenon.

By the end of the proposed project we expect to have demonstrated the feasibility of HP xenon

MRI detection of human BAT mass and thermogenic activity. These studies will also provide preliminary data for powering a future clinical trial with which we aim to investigate the incidence and activity of this tissue in the human population.

**SIGNIFICANCE:** Most of our knowledge on BAT comes from animal studies. In small animals we know that BAT prevents obesity and improves and reverses insulin insensitivity. In humans the role of this tissue is less clear. This is because human BAT studies have been limited mainly to retrospective studies on cancer patients due to lack of safe and reliable detection techniques to study the small quantities of diffusely distributed BAT depots present in humans *in vivo*. Fusion FDG-PET/CT remains the gold-standard imaging modality for non-invasive studies of metabolically active BAT. However, this technique is intrinsically insensitive to BAT metabolism as only small amounts (less than 10%) of glucose are taken up by activated BAT. The rest of the substrate (more than 90%) is made by fatty acids released from intracellular lipid storages. As such, the activity of this tissue is clearly underestimated by FDG-PET scans. This is especially true for overweight and obese subjects, the target population for BAT, in whom the intracellular lipid storage is more abundant (brown fat cells are swollen with fat) than in lean subjects. Therefore, this tissue relies even less on circulating glucose for thermogenesis, further limiting its detectability by FDG-PET scans. More importantly, the elevated risk of ionizing radiation and radionuclide tracer radiation exposure from these scans precludes repetitive BAT screening in healthy and young subjects, scans which are needed to correctly estimate the true prevalence of BAT, to determine the physiological relevance of BAT in humans, and to test the efficacy of new anti-obesity treatments. With this proposal we aim to fulfill this need. HP xenon MRI is extremely sensitive to the more lipid rich and less thermogenically active BAT of obese phenotypes (see comparison with FDG-PET in Fig 1) and, by being non invasive, can be repeatedly used on healthy subjects to track BAT function over time. In addition it allows direct measurement of BAT cell temperature (Fig. 2) and therefore represents the only direct way we have to monitor BAT thermogenic activity.

[figure not shown]
**INNOVATION:** MRI with hyperpolarized xenon-129 is a technique that is been used extensively in humans to detect lung ventilation function. Here we propose for the first time to use hyperpolarized xenon gas MRI to detect BAT. Xenon is an ideal BAT probe for several reasons: A) the solubility of xenon in fatty tissue is 10 times higher than in lean tissues or blood. This means that circulating xenon naturally diffuses into BAT, enabling adequate SNR for imaging. B) Xenon is an ideal blood perfusion tracer, and therefore ideally suited to detect the increase in blood flow to BAT that occurs during stimulation of BAT thermogenesis. C)

Because xenon is not intrinsic to biological tissue, HP  $^{129}\text{Xe}$  can produce background free maps of human BAT. D) The temperature sensitivity of lipid-dissolved xenon will enable us to directly measure BAT temperature and monitor thermogenic activity in real time.

*This research is innovative as it uses an entirely different approach to investigate BAT. To our knowledge we are the very first group to use hyperpolarized xenon gas to detect BAT mass and to have demonstrated HP xenon MR thermometry of fatty tissues.*

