**APPROACH: Aim1: Demonstrate BAT mass detection in human subjects.**

Our extensive preliminary studies in rodents have shown that, upon stimulation of BAT thermogenesis, an enhancement of more than 10-fold of the MR signal from xenon dissolved in BAT is observed. This enhancement is such that a background free map of this tissue can be obtained in just few seconds (Fig. 1). In addition, when compared to FDG-PET images of BAT, hyperpolarized xenon gas images were able to clearly show BAT in both lean and obese mice and, in the latter, with superior sensitivity (Fig.1b-d).

[figure not shown]
**Fig. 1** Detection of interscapular BAT by hyperpolarized xenon gas MRI (a-b) and FDG-PET (c-d) in a lean (a-c) and obese (b-d) animal. Hyperpolarized xenon gas is clearly more sensitive to the lipid-rich BAT of obese animals (b) than FDG-PET. In d) glucose uptake by BAT is substantially reduced, making it difficult to differentiate BAT from the surrounding tissue.

The broad aim of this proposal is to validate this completely new approach to detect BAT in humans. To this end we will perform HP  $^{129}\text{Xe}$ -MRI of BAT on a 3T clinical magnet using a dual tuned xenon/1H surface coil recently purchased for human BAT studies. The coil will be accurately located above the suprACLAVICULAR area to increase sensitivity to the xenon signal dissolved in the tissue beneath. Conventional  $^1\text{H}$  MRI, which will provide anatomical reference images, will be followed by HP  $^{129}\text{Xe}$  spectroscopy and imaging scans, similar to those used in our rodent studies. Before the acquisition of the xenon images, the subject will be asked to inhale a 1L bag of 100% hyperpolarized and enriched xenon from a Tedlar bag and to hold his breath for about 15-20s. During this time hyperpolarized xenon gas will diffuse from the lung airspaces to BAT in a perfusion-based manner. At the end of the 10 s from the beginning of gas inhalation we will trigger the acquisition of the MR image, which will last for about 10s. The

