This feasibility study will allow us to estimate the standard deviation for the increase in signal from xenon dissolved in BAT and for the increase in BAT temperature that will then be used to power future trials to investigate the incident of this tissue in the healthy human population and the association between BMI and BAT thermogenic activity. For these aims we plan on enrolling a total of 24 healthy subjects (12 for aim 1 and 12 for aim 2) with a BMI ranging between 18 and 28. Twelve is the minimum sample size recommended in the absence of prior information on which to base our sample size calculation. With 12 subjects per group we should be able to obtain positive results (with a 95% confidence interval) on at least 9 subjects if the true prevalence of BAT is 90% (expected prevalence), and on at least 3 subjects if the true prevalence of BAT is much smaller and close to 50% (estimated by FDG-PET scans).

By the end of the study we expect to have fully assessed the potential of HP xenon to detect BAT mass and activity and to have developed an imaging protocol that can be used in studies aimed to investigate the prevalence of this tissue in humans, its connection with other metabolic diseases such as diabetes, and to study the response to treatments aimed to counteract obesity by increasing BAT mass and or function.

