#### **A. Proposed involvement of human subjects**

All research involving human subjects will be carried out at the University of North Carolina at Chapel Hill. All MRI experiments will take place in the Biomedical Research Imaging Center, where the PI's lab for hyperpolarized  $^{129}\text{Xe}$  gas MRI and the 3T Siemens MRI scanner is located. A medical technician, with knowledge and skills consistent with those provided in the American Heart Association's Advanced Cardiac Life Support training will observe the subjects whenever they are breathing xenon gas. Supplemental oxygen (adjusted to flow at 4 liters/minute), suction source, bag valve mask, ventilation device and an airway support device will be available in the MR scanner room. During scanning, a MRI compatible pulse oximeter will be used to monitor the subject's heart rate and blood oxygenation.

A total of 24 healthy subjects, without any metabolic disease, of ages 18 to 40 will be recruited to participate. All subjects will undergo hyperpolarized xenon-129 MR. Healthy subjects are considered those who have never been diagnosed with metabolic diseases, and have no history of any chronic lung disease such as asthma, COPD, or CF.

Since our aim is devoted to test the efficacy of the new methodology for the detection of BAT, there is no justification to scan children under 18 years old. Pregnant or lactating women will be excluded due to potential health risks. All subjects must be able to undergo an MRI examination (e.g., no MRI incompatible implanted devices or other MR contra-indications).

[name] will be present during all hyperpolarized xenon-129 MR scans.

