#### Source of material

The research material obtained from the subjects will be the results of MR studies. This information will be used solely for research.

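### The stated objective is validation in humans, but with no independent measure of BAT in any subject the study can show feasibility of detecting a signal change, not that the signal is BAT

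*Combined protocol and SAP*

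**What the plan says.** **Objective.** The Specific Aims state: "The objective of the current proposal is to validate this technique in humans". The Approach, Aim 1, repeats it: "The broad aim of this proposal is to validate this completely new approach to detect BAT in humans". The last paragraph of the Approach adds that "we expect to have fully assessed the potential of HP xenon to detect BAT mass and activity".

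**Feasibility.** The final paragraph of the Specific Aims promises a demonstration of feasibility and preliminary data to power a later trial. The sample-size paragraph at the end of the Approach calls this a feasibility study whose product is standard deviations for later trials.

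**Measurements.** Section A says: "All subjects will undergo hyperpolarized xenon-129 MR". Source of material says: "The research material obtained from the subjects will be the results of MR studies". The only other imaging is conventional proton MRI, "which will provide anatomical reference images". On reference methods, the Specific Aims say: "The current gold standard for the detection of BAT activity is FDG-PET". FDG-PET is not scheduled in any subject; the comparison with it in Fig. 1 is in animals.

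**Definition of a positive.** Under Aim 1, detectable BAT volume is the volume of pixels whose xenon intensity rises by more than 5% on cooling. Under Aim 2, BAT temperature is derived from the xenon resonance frequency alone.

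**Expected counts.** The sample-size paragraph and section F (Number Justification) expect, with 12 subjects per aim, at least 9 positives if BAT prevalence is 90% and at least 3 if it is about 50%.

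**The concern.** Validating a detection method means showing that what it calls positive has the target and that what it calls negative does not. That needs information about the target from outside the method. Here the method under test also supplies the definition of the target, so a positive subject is one in whom the xenon signal or frequency changed on cooling, and nothing more.

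At stake is how the headline count will be read. Ten or eleven positives out of 12 would invite the statement that the technique is validated and that BAT is present in most healthy adults. The sample-size text prepares that reading by setting counts of positives directly against prevalence.

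**Working it through.** **1. Is there a second measure of BAT?** The Approach, section A and Source of material together give xenon MR and proton MRI. Proton MRI is used for anatomy, and the Specific Aims themselves describe MRI as lacking specificity for BAT. The budget table agrees: 8,640 + 19,968 + 12,240 + 1,440 = 42,288, the stated total, with no line for PET or biopsy. In the text available for review, no subject has an independent measure.

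**2. The plan's own counts.** Inputs: n = 12; prevalence 90% or 50%; 95% confidence. Let X be binomial, with the positive rate set equal to prevalence.

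- At 0.90: P(X ≥ 9) = 0.0852 + 0.2301 + 0.3766 + 0.2824 = 0.974, and P(X ≥ 10) = 0.889.
- At 0.50: P(X ≥ 3) = 1 − (1 + 12 + 66)/4096 = 0.981, and P(X ≥ 4) = 0.927.

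So 9 and 3 are the largest counts reached with at least 95% probability. Both figures reproduce as one-sided 95% bounds.

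**3. What those counts assume.** In general

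positive rate = prev × sens + (1 − prev) × (1 − spec).

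Setting this equal to prevalence at both planned values gives 0.9·sens + 0.1·(1 − spec) = 0.9 and 0.5·sens + 0.5·(1 − spec) = 0.5. The second gives 1 − spec = 1 − sens. Substituting in the first gives 0.8·sens = 0.8, so sens = 1 and spec = 1. Both counts follow from prevalence together only for a perfect test.

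**4. What a high count can mean.** The combinations below are illustrative assumptions, not figures from the plan.

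| Prevalence | Sensitivity | Specificity | Positive rate |
|---|---|---|---|
| 75% | 100% | 100% | 0.75 |
| 90% | 83.3% | 100% | 0.90 × 0.833 = 0.75 |
| 50% | 100% | 50% | 0.50 + 0.50 × 0.50 = 0.75 |
| 90% | 100% | 100% | 0.90 |
| 50% | 100% | 20% | 0.50 + 0.50 × 0.80 = 0.90 |

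The first three rows cannot be told apart by the count, nor can the last two, each of which gives the same 0.974 chance of 9 or more positives. The assumption also affects the planned count. In the second row prevalence is the expected 90%, yet P(X ≥ 9 at 0.75) = 0.2581 + 0.2323 + 0.1267 + 0.0317 = 0.649, not 0.974.

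**5. What a low count can mean.** Whatever the specificity, the positive rate is at least prev × sens. With 0 of 12 positive, the two-sided 95% Clopper-Pearson upper limit is 1 − 0.025^(1/12) = 26.5%. Sensitivity is then at most 0.265/0.5 = 53% at 50% prevalence and 0.265/0.9 = 29% at 90%. Equally, with a perfect test and 50% prevalence, 2 or fewer positives has probability 79/4096 = 0.019. A very low count is therefore informative if prevalence lies in the plan's range.

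**The case against.** **The study is a feasibility study and says so.** This stands in part. The feasibility outcome and the standard deviations can be delivered without a reference, and the last paragraph of the Approach speaks of the potential of the method, which is looser than an accuracy claim. But the objective and the broad aim are still stated as validation, and the two descriptions need reconciling.

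**The data bear on tissue identity indirectly.** Aim 1 scans are taken before and during cooling, the coil lies over the supraclavicular area, proton anatomy is available, and Aim 2 looks for a temperature change. This makes a BAT origin more plausible. It does not establish it, and it says nothing about whether a negative subject lacks BAT.

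**FDG-PET would be a poor reference.** The radiation argument, that exposure "precludes repetitive BAT screening in healthy and young subjects", concerns repeated scans. But the plan also calls FDG-PET irreproducible, insensitive to BAT metabolism and unable to find BAT in overweight and obese subjects. Those objections apply to a single scan too, so a reader should not infer that its omission is unexplained. A doubtful reference is a reason not to claim validation; it does not replace a reference.

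**Stronger readings to avoid.** A reader might infer that no count, high or low, could bear on the method. The last step of the working shows otherwise for low counts. A reader might also infer that the plan will estimate sensitivity and specificity or compare humans with FDG-PET. No such analysis is planned; FDG-PET enters the human part only as the source of the 50% prevalence figure.

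**Conclusion.** The point holds as a mismatch between the stated objective and what the data can show. A high count of positives cannot establish that the signal is BAT, nor give its prevalence, and a negative subject cannot be shown to lack BAT. A very low count would count against the method if prevalence is between 50% and 90%, as the plan assumes.

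The 9-of-12 and 3-of-12 figures are arithmetically right (0.974 and 0.981) under a perfect test, a condition the study cannot examine. How far true accuracy departs from perfect is unknown; the combinations in the table show that the count cannot separate the possibilities, not that any of them is likely.

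This does not make the study unsound or require a reference scan. Even with a reference in all 12 subjects of one aim and perfect agreement, the 95% lower limits with 6 BAT-positive and 6 BAT-negative subjects would be 0.025^(1/6) = 54% for both sensitivity and specificity. With 11 and 1 they would be 0.025^(1/11) = 72% and 2.5%. The feasibility aim fits the design; the validation aim does not.

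**What to change.** 1. In the Specific Aims and in the Approach, Aim 1, replace the aim of validating the technique with assessing the feasibility of detecting a cold-induced change in supraclavicular dissolved-xenon signal and frequency. Limit the concluding paragraph of the Approach to match.
2. Report the number of positive subjects as a detection rate (cold-induced change seen or not seen), not as BAT present or absent and not as prevalence.
3. In the sample-size paragraph and in section F, state that the expected counts of 9 and 3 assume 100% sensitivity and 100% specificity.

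The cost is a less favourable conclusion. Design, scans and number of subjects are unchanged.

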**APPROACH: Aim1: Demonstrate BAT mass detection in human subjects.**

Our extensive preliminary studies in rodents have shown that, upon stimulation of BAT thermogenesis, an enhancement of more than 10-fold of the MR signal from xenon dissolved in BAT is observed. This enhancement is such that a background free map of this tissue can be obtained in just few seconds (Fig. 1). In addition, when compared to FDG-PET images of BAT, hyperpolarized xenon gas images were able to clearly show BAT in both lean and obese mice and, in the latter, with superior sensitivity (Fig.1b-d).

[figure not shown]
**Fig. 1** Detection of interscapular BAT by hyperpolarized xenon gas MRI (a-b) and FDG-PET (c-d) in a lean (a-c) and obese (b-d) animal. Hyperpolarized xenon gas is clearly more sensitive to the lipid-rich BAT of obese animals (b) than FDG-PET. In d) glucose uptake by BAT is substantially reduced, making it difficult to differentiate BAT from the surrounding tissue.

The broad aim of this proposal is to validate this completely new approach to detect BAT in humans. To this end we will perform HP  $^{129}\text{Xe}$ -MRI of BAT on a 3T clinical magnet using a dual tuned xenon/1H surface coil recently purchased for human BAT studies. The coil will be accurately located above the suprACLAVICULAR area to increase sensitivity to the xenon signal dissolved in the tissue beneath. Conventional  $^1\text{H}$  MRI, which will provide anatomical reference images, will be followed by HP  $^{129}\text{Xe}$  spectroscopy and imaging scans, similar to those used in our rodent studies. Before the acquisition of the xenon images, the subject will be asked to inhale a 1L bag of 100% hyperpolarized and enriched xenon from a Tedlar bag and to hold his breath for about 15-20s. During this time hyperpolarized xenon gas will diffuse from the lung airspaces to BAT in a perfusion-based manner. At the end of the 10 s from the beginning of gas inhalation we will trigger the acquisition of the MR image, which will last for about 10s. The

same protocol will be followed during stimulation of BAT thermogenesis, which will be achieved by an MR compatible water cooling-blanket ( $\sim 15^{\circ}\text{C}$  circulating water temperature), which will be positioned on the lower abdomen/upper leg part of the subjects. The ability to detect BAT by hyperpolarized xenon gas relies on the enhancement in blood flow to this tissue that occurs during stimulation of thermogenic activity. The magnitude of this enhancement seems to be the same, irrespective of the species and of the modality of stimulation of BAT thermogenesis (NE injection of mild cold exposure). Therefore we expect to detect a similar enhancement in the MR signal from xenon dissolved in human BAT. In addition, the use of enriched xenon versus naturally abundant xenon will compensate for the possible loss in xenon polarization during blood transit time. Pre and post stimulation scans will be compared with Matlab to detect differences of more than 5% in the intensity of the dissolved phase xenon images. Detectable BAT volume will be calculated as the sum of pixels whose intensity rose by more than 5% during cold stimulation multiplied by the pixel volume ( $1 \text{ mm}^3$ ). Data will be analyzed using JMP Pro-9.0.0 software (SAS Institute). All P values presented will be two-tailed, and values less than 0.05 will be considered to indicate statistical significance. According to previous studies done in human brain and considering the increase in blood perfusion that occurs in BAT during cold stimulation as well as the higher solubility of xenon in fatty tissues, we expect to be able to obtain images with a resolution of  $0.3 \times 0.3 \text{ cm}$ , high enough to differentiate BAT from the surrounding tissues.

**Aim 2:** Demonstrate detection of BAT thermogenesis in humans.

Dynamic spectroscopy data have shown the possibility to track BAT temperature over time by measurement of the chemical shift of lipid-dissolved xenon. We demonstrated for the first time MR thermometry by hyperpolarized xenon gas. This method is based on the temperature dependence of the chemical shift of lipid dissolved xenon, which we measured for the first time *in vivo* to be  $-0.2 \text{ ppm}^{\circ}\text{C}$ , (Fig 2.a), i.e. 20 times larger than that of water protons currently used for MR thermometry in lean tissues. This higher sensitivity of lipid-dissolved xenon to temperature, coupled with the lower gyromagnetic ratio of xenon (which makes xenon less sensitive to possible magnetic field in homogeneities present in fatty tissues), allowed us to detect BAT thermogenic activity in mice (Fig.2.b). To this end we will acquire dynamic spectroscopy data from xenon dissolved in BAT during stimulation of BAT thermogenesis by mild cold exposure. During these scans we will track the resonance frequency of lipid-dissolved xenon to detect changes in BAT temperature during thermogenic activity. Although in humans we expect temperature changes less than  $2^{\circ}\text{C}$ , the high sensitivity of xenon to temperature and the narrow line width can allow us to detect changes as small as  $0.2^{\circ}\text{C}$ .

**Fig.2** a) Linear temperature shift of the lipi-dissolved xenon frequency as acquired *in vivo* in an obese mouse. b. Thermogenic activity as detected by hyperpolarized xenon gas. The graph shows the resonance frequency shift of lipid-dissolved xenon and the corresponding shift in BAT temperature right after injection of NE.

For these studies the subject will inhale 4 doses of 1L each of xenon during mild cold exposure, achieved with a water cooling blanket. After inhalation, the subject will be asked to hold his breath for 15-20 seconds, during which we will trigger the acquisition of xenon spectra. The spectra will then be fitted with homemade Matlab routines to extract lipid-dissolved xenon resonance frequency that will be used to detect any change in BAT temperature.

The change in BAT temperature will then be analyzed as function of BMI to establish whether or not there is an association between BMI and BAT temperature increase (Pearson correlation and Spearman correlation coefficient calculation).

This feasibility study will allow us to estimate the standard deviation for the increase in signal from xenon dissolved in BAT and for the increase in BAT temperature that will then be used to power future trials to investigate the incident of this tissue in the healthy human population and the association between BMI and BAT thermogenic activity. For these aims we plan on enrolling a total of 24 healthy subjects (12 for aim 1 and 12 for aim 2) with a BMI ranging between 18 and 28. Twelve is the minimum sample size recommended in the absence of prior information on which to base our sample size calculation. With 12 subjects per group we should be able to obtain positive results (with a 95% confidence interval) on at least 9 subjects if the true prevalence of BAT is 90% (expected prevalence), and on at least 3 subjects if the true prevalence of BAT is much smaller and close to 50% (estimated by FDG-PET scans).

By the end of the study we expect to have fully assessed the potential of HP xenon to detect BAT mass and activity and to have developed an imaging protocol that can be used in studies aimed to investigate the prevalence of this tissue in humans, its connection with other metabolic diseases such as diabetes, and to study the response to treatments aimed to counteract obesity by increasing BAT mass and or function.

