#### Hyperpolarized xenon-129 MRI:

Subjects will be positioned supine within the MR scanner. The dual tuned xenon/proton surface coil will be positioned above the supraclavicular area. After breathing normally for a few minutes, the subject will exhale completely to residual volume, and then inhale a 1-L volume of undiluted hyperpolarized xenon-129, followed by a breath-hold lasting from 10-15 s during and after which imaging will be performed. The subject will then exhale fully and breathe normal air. Xenon doses will be administered no less than 15 minutes apart. During the MRI exam, oxygen saturation, heart rate, and blood pressure will be continuously recorded. These parameters, along with respiratory rate and subjective symptoms, will also be assessed after each dose. Immediately after inhalation, the subject will also be asked to report any symptoms or effects from xenon.

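### One fixed cold stimulus, with no planned record of shivering or of the cold received, leaves the BMI correlation and the Aim 1 volume open to explanations other than BAT

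*Combined protocol and SAP*

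**What the plan says.** **Stimulus.** Under Aim 1 in APPROACH, stimulation is one "which will be achieved by an MR compatible water cooling-blanket" set-up, at about 15 °C "circulating water temperature", "which will be positioned on the lower abdomen/upper leg part of the subjects". Under Aim 2 the subject inhales xenon "during mild cold exposure, achieved with a water cooling blanket"; temperature and site are not repeated, and no other set-up is described. The supplied text states no exposure time, individual adjustment, or skin or core temperature measurement.

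**Monitoring.** The section Hyperpolarized xenon-129 MRI lists oxygen saturation, heart rate and blood pressure throughout, with respiratory rate and subjective symptoms after each dose. It adds: "Immediately after inhalation, the subject will also be asked to report any symptoms or effects from xenon". Shivering and cold received are not named.

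**Read-outs.** Aim 1 detection "relies on the enhancement in blood flow to this tissue that occurs during stimulation of thermogenic activity". BAT volume is the number of pixels that brighten by more than 5% under cooling, times the pixel volume; no tissue mask is stated. Aim 2 uses the resonance frequency of lipid-dissolved xenon.

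**Analysis.** The Aim 2 temperature change is correlated with BMI (Pearson and Spearman, unadjusted) to "establish whether or not there is an association between BMI and BAT temperature increase". The closing part of APPROACH gives 12 subjects per aim and a BMI range of 18 to 28. It says the standard deviations obtained will be used to power later trials, including one on BMI and BAT thermogenic activity.

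**The concern.** The blanket covers a region where the fat layer may differ between a subject at BMI 18 and one at BMI 28. If it does, the same water temperature need not be the same effective stimulus. A smaller temperature rise at one end of the BMI range could then mean less BAT activity, less cold received, or both. With nothing recorded about the cold received, no later analysis can tell these apart.

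Shivering is a second and separate problem. It raises muscle blood flow and heat and moves the subject. In Aim 1, a muscle pixel that brightens by more than 5%, or tissue that shifts between scans, would be counted as BAT. In Aim 2, heat or motion could affect the spectra. If shivering is not noted at the time, the affected scans cannot be identified afterwards.

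At stake are how the BMI association is read, the Aim 1 volume and count of positive subjects, and how much of the standard deviation passed to later trials is variation in stimulus.

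**Working it through.** **1. The plan's own figure.** The only stated statistical figures are the counts of positive subjects out of 12. By exact binomial, P(X ≥ 9 | 0.9) = 0.974 and P(X ≥ 10 | 0.9) = 0.889; P(X ≥ 3 | 0.5) = 0.981 and P(X ≥ 4 | 0.5) = 0.927. So 9 and 3 are the largest counts reached with at least 95% probability, and the figures reproduce. They do not bear on this point. No power or precision is stated for the BMI correlation.

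**2. What the correlation can show.** Inputs: n = 12, two-sided 0.05 (both in APPROACH).
- Critical |r| = t/√(t² + df). With df = 10, t = 2.228: 2.228/√(4.965 + 10) = 0.576.
- Power: 16% at a true r of 0.3, 40% at 0.5, 78% at 0.7.
- 95% interval around an observed r of 0: ±tanh(1.96/√(12 − 3)) = ±0.57.

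**3. Effect of an unrecorded stimulus difference.** The documents give no value linking BMI to cold received or cold received to temperature, so a range is assumed. Let X be standardised BMI, D cold received and Y temperature change:
- D = −aX + √(1 − a²)·e₁
- Y = bD + √(1 − b²)·e₂

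BMI has no direct effect on Y, and the induced correlation is −ab. The negative sign is also assumed; the two-sided rejection rate is the same for either sign. Simulated at n = 12:

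| a = b (assumed) | induced r | P(significant) |
|---|---|---|
| 0 | 0 | 5% |
| 0.3 | −0.09 | 6% |
| 0.5 | −0.25 | 12% |
| 0.6 | −0.36 | 21% |
| 0.7 | −0.49 | 38% |
| 0.8 | −0.64 | 66% |

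**4. What recording the cold would buy.** Partial correlation on D, same model:
- D recorded without error: 5.0% at every link tried (0.5, 0.7, 0.8).
- D recorded with reliability 0.7: 6% at links of 0.5, 10% at 0.7, 18% at 0.8.
- Cost: df falls to 9 and the critical |r| rises to 2.262/√(5.117 + 9) = 0.602.

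**5. Shivering, by read-out.**
- *Aim 1.* INNOVATION describes xenon as a blood-flow tracer about ten times more soluble in fat than in lean tissue. Muscle therefore gives less signal, but the 5% rule is relative. A muscle pixel above the noise can pass it if its flow rises, and so can a pixel displaced by motion.
- *Aim 2.* The signal is lipid-dissolved xenon, so muscle acts only through local heat, warmed blood or motion. The margin is small: at −0.2 ppm/°C, the 0.2 °C said to be detectable is 0.2 × 0.2 = 0.04 ppm, and the expected upper limit of 2 °C is 0.4 ppm.

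**The case against.** The case against giving this much weight is substantial.

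- *The correlation is imprecise anyway.* It is one analysis in 12 subjects, and Aim 2's purpose, detecting thermogenesis, does not depend on it. This stands and limits the size of the point. It does not help with a quantity that can only be recorded during the scan.
- *Subjects are watched.* Section A puts a medical technician in attendance whenever xenon is breathed, heart rate is recorded, and subjective symptoms are assessed after each dose. Shivering might well be noticed. What is missing is a planned, recorded item; the question asked straight after inhalation concerns effects of xenon.
- *The plan asks only about an association.* Cold received lies on the path from BMI to temperature, so the unadjusted correlation is a fair description of the response to this blanket. It misleads only if read as BAT activity by BMI, which is the question named for the later trial.
- *The stimulus is called mild,* and nothing in the documents shows that it causes shivering. This stands: shivering is a possibility to record, not an expected event.

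Four stronger readings are tempting and are not supported.

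- A reader might infer that leaner subjects do receive more cold, so that a negative association would appear. The documents hold no data on fat thickness or cold response by BMI, and at assumed links of 0.3 the false-positive rate barely moves.
- A reader might put a number on it by steady conduction: 0.2 W/m/K × 17 °C gives 340 W/m² through 1 cm of fat and 113 W/m² through 3 cm, a 3-fold difference. Every input is assumed and no thickness is tied to BMI 18 or 28. The result is regional heat loss with skin held equally cold, not thermogenic stimulus.
- A reader might conclude that the later trial would be built on a biased slope. The plan carries forward standard deviations. They would include variation in stimulus, which is appropriate if the later trial cools in the same way.
- A reader might expect shivering muscle to drive the BMI correlation. That correlation uses the lipid-xenon frequency, which muscle reaches only indirectly; the more direct exposure is in Aim 1, where no BMI analysis is planned.

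**Conclusion.** The point holds as a gap in what is recorded and a limit on interpretation. One cooling set-up is described, neither shivering nor cold received is recorded by plan, and the BMI correlation is unadjusted. That correlation could partly reflect differences in effective stimulus, in a direction and size that cannot be taken from the documents. On assumed links the false-positive rate runs from 6% to 66%; it reaches about 20% or more only if both links are about 0.6 or stronger. Separately, shivering could add non-BAT pixels to the Aim 1 volume and could disturb the Aim 2 spectra indirectly; neither effect can be sized from the documents.

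This assumes that the Aim 1 blanket setting also applies in Aim 2, which is reasonable but not written, and that the supplied text is complete on monitoring. The remedy is worth making because it is cheap and the information cannot be recovered after the scans.

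**What to change.** No change to the cooling procedure is proposed.

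1. At each xenon dose, add two items to the existing assessment: shivering (yes/no), noted by the observer already present, and a cold rating given by the subject.
2. Report the Aim 1 volume and positivity, and the Aim 2 temperature change, with and without shivering-flagged scans. Treat this as a sensitivity analysis, not an automatic exclusion, and show the BMI of flagged subjects.
3. Report the BMI correlation as exploratory, with a confidence interval, and with and without adjustment for the cold rating. State that the rating measures sensation and is an imperfect proxy for cold received, so the adjusted result is secondary.
4. Describe the correlation as the response to a fixed external stimulus.

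Cost: two form items and a few extra lines of analysis, with no new staff or procedure. The sensitivity results will be slightly less precise. If leaner subjects shiver more, leaving out flagged scans would lose them selectively, which is why the full-data result stays alongside.
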